Provided inclusion criteria are met, referrals will be scheduled for a telephone follow-up and scheduling for the first study. Individuals meeting eligibility criteria will be then be invited to the Coral Gables campus for an in-person COVID-19 and urine toxicology screening, prior to enrollment.

This study will actively recruit participants through the Community Outreach Core and Clinic Registry Project for the Center for HIV and research in Mental Health (CHARM) (IRB#20160911) of the University of Miami Center for AIDS Research. This mechanism allows IRB-approved study investigators the ability to search and identify potential willing research participants who meet study criteria. Upon contact, patients will verify their identity before being informed about the study and moving forward with the screening process. Patients will also be informed they have the right to change their consent in order to decline to be contacted for future studies.

Participants will also be recruited from the Miami MWCCS E-Prost Protocol No. 20210476, a study of men and women living with HIV in the US. The MWCCS has approved a concept sheet to refer MWCCS participants to this study. MWCCS participants who meet inclusion criteria will be asked by the MWCCS team, for willingness to participate in this study. Those interested participants will be given the contact information to contact the study directly, or if they prefer, their contact will be shared with study staff to contact them and provide information about the study.

Exclusion criteria. Following initial referral, participants will be assessed for PTSD over the phone through the primary care PTSD screen for DSM-5 (PC-PTSD-5) (64). After the participant has consented an in-house screener will also be used to assess substance dependency, suicidal ideation, history or treatment for schizophrenia or bipolar disorder, as well as severe dementia indexed by the Mini-Mental State Examination (MMSE) (65). Additional exclusion criteria include the following: 1) Left-handedness or ambidextrous; 2) Inability to tolerate the scanning procedures (e.g., claustrophobia); 3) Metal in body or prior history working with metal fragments (e.g., as a machinist); 4) Any other contraindications for MRI examination (e.g., metallic implants such as pacemakers, surgical aneurysm clips, or

IRB Study Number: 20190760

Version: 10 Date: 06/06/2022

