known metal fragments embedded in the body); 5) currently pregnant or could be pregnant ; 6) Heavy alcohol intake (> 3 drinks) within 12 hours prior to participation in fMRI ; 7) Evidence from health history of neurological or systemic disorder which can cause cognitive impairment; 8) Self-reported current diagnosis of psychiatric disorder or psychoactive substance abuse or dependence; 9) Recent history (within two years) of myocardial infarction; 10) Severe cardiovascular disease, or currently active cardiovascular disease (e.g., angina, cardiomyopathy); 11) Uncontrolled hypertension or hypotension; 12) History of closed trauma with loss of consciousness; 13) Space occupying lesions (e.g., mass lesions, tumors); 14) CNS infection; 15) CNS vasculitis; 16) CNS demyelinating disease (e.g., multiple sclerosis); 17) Congenital CNS abnormality (e.g., cerebral palsy); 18) Seizure disorders; 19) History of cerebrovascular disease (e.g., stroke, TIA's)

Inclusion criteria. 1) Age \geq 21 years; 2) Elevated PTSD symptoms as assessed by the PCL-5 using a cut-off of 34 or above. This measure has been validated using the gold standard against the goal standard for PTSD, i.e., Clinician-administered PTSD scale for DSM-5 (CAPS-5) (66, 67). Although the current gold-standard, i.e., DSM-5 has not been translated to Spanish, if this is not available at the time of study we will revert back to the Spanish version of the PCL-C adapted for DSM-IV (68). The Davidson Trauma Scale (DTS) will be used as a back-up to identify DSM-IV symptoms for post-traumatic stress disorder (PTSD); 3) on a stable anti-retroviral therapy regimen for > 6 months as assessed with the Adult AIDS Clinical Trial Group structured interview (69); 4) Spanish-English bilingual as measured by the Brief Acculturation Scale for Hispanics (cut-off of 3), Spanish speaker or English speaker 5) Participant is willing and able to sign ICF; 6) self-report as Latina (i.e. self-reported); 7) HIV positive serostatus as determined by medical record within the last 12 months; 8) born female.

7) Study Design

a) Primary purpose

To determine whether in (LLWH) exposure to an expressive writing intervention in Spanish will have an effect on primary and secondary study outcomes.

b) Interventional study model

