Randomized control trial with participants randomized to either the augmented trauma-writing intervention in English, the augmented trauma-writing intervention in Spanish or the daily-event-writing control in English/Spanish. Both experimental and control participants will visit the study on four occasions during a 4-week period so that they could write for 30 min in a private office.

8) Procedures

General overview. Upon meeting all eligibility criteria individuals will be consented into the study. Full participation in the study will involve 6 separate session. The first

IRB Study Number: 20190760

Version: 10 Date: 06/06/2022

and sixth sessions will last approximately 4-5 hours. On the evening prior to these sessions participants will perform an overnight fast and told to avoid drugs, alcohol and exercise. On the mornings of session 1 and 6 participants will report to the Cox Neuroscience Annex (CNA). Participants will be compensated \$80 each for the pre- and post-intervention sessions. Participants will also receive \$20 for attending each online writing session. Each participant will be compensated using the Zelle™ mobile banking application.

Screening. Prior to informed consent individuals will undergo screening using the 5-item PTSD checklist (PC-PTSD-5) in order to determine their eligibility to participate in the study. This is required given trauma interventions can potentially have adverse effects on asymptomatic individuals. . After the initial screening, referrals will be instructed to bring a copy of their most recent HIV labs (drawn within the last 6 months) for their in-person screening session, if they are HIV+. Labs will not be requested for the HIV- participants. After obtaining informed consent, we will make a copy of those labs, remove any identifiable information, and return the original copy to the research participant.

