Pre- and post-intervention Sessions 1b and 6b (post-scan assessments). Following the blood draw (T2), participants will be escorted to a separate room. Within this room, they will be fitted with electrodes for measurement of heart rate, respiratory rate and blood pressure during the completion of a behavioral self-compassion task. This task will take approximately 30 minutes to complete. Following completion of this task a third blood draw (T3) will be performed and (2) 20ml tubes will be collected for immediate processing. Following the compassion task a battery of psychosocial and neurocognitive measures will be administered lasting approximately 90 – 120 minutes. The estimated time of completion for all Session 1a & 6a activities is 4 hours per session. Participants will complete a psychosocial battery of self-report questionnaires using a laptop or personal computer (See Table 1). Following the surveys participants will engage in an exit interview.

Sessions 2-5: Arms and Interventions.

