Each encoding block is followed by a distracter epoch (19.5 s), where participants attend to a series of letters (i.e., “XXXXX—YYYYY”) to mimic the active stimulus. This is included to discourage rehearsal. Participants pressed with their right index finger when they saw the letters to control for motor activity in the other conditions. Immediately after each distracter epoch was a 19.5 s recall epoch, during which participants saw the first word of each pair from the encoding epoch that preceded it (e.g., UP - ___), attempted to recall the second word silently (3 s), and viewed a black screen (0.9 s). Subjects indicate perceived success at recalling the second word with a right index finger response and perceived failure with a left index finger response. After each recall epoch, participants focused on a crosshair (6 s) to allow for brain activity to return to its baseline. The sequence of encoding epoch, distractor epoch, and recall epoch repeated ten times. Before each new epoch began, there was a 3 s prompt to inform the participant which task they would need to perform. The full presentation of the task will last 12 m and 24 s.

The following neuropsychological tests and surveys will be administered during session 1 and 2. All forms are submitted and approved by IRB. Each assessment takes between 5 and 15 minutes to complete.

IRB Study Number: 20190760

Version: 10 Date: 06/06/2022

Table 1. Schedule of Assessments

Domain	Measure	T0 screen	T1 pre	T2 write	T3 write	T4 write	T5 write	T6 post
Cognitive	Mini-mental State Exam screener		X					
Psychiatric	Mini-International Neuropsychiatric Interview		X					
	Treatment Outcome PTSD Scale (TOP-8)		X					X
	PTSD Checklist for DSM-5 (PCL-5)		X					
	Civilian Spanish-English version PCL-C		X					
Acculturation	Brief Acculturation Scale For Hispanics (BASH)		X					
	Bidimensional Acculturation Scale (BAS)		X					
Psychosocial	Subjective Unit of Distress		X	X	X	X	X	X
	Impact of events scale—revised		X					X
	Spielberger State-Trait Anxiety Scales		X					X
	Anxiety Sensitivity Index		X					X
	Beck Depression Inventory		X					X
	Toronto Alexithymia Scale		X					X
	Multidimensional Interoceptive Awareness Scale		X					X
	Dissociative Experiences Scale		X					X
	Early Trauma Inventory		X					X
	Perceived Support Network Inventory		X					X
	Brief COPE		X					X
	*Brief Symptoms Inventory		X					X

IRB Study Number: 20190760

Version: 10 Date: 06/06/2022

	*Center Epi- Studies Depression Scale		X					X

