Upon arrival at the University of Miami Downton and Coral Gables locations there will be no additional costs for which the participants will be responsible. In addition, participants will be offered water and light snacks throughout the two sessions.

29) Consent Process

This study will follow the UM standard operating procedure for the Informed Consent Process for Research (HRP-090). The consent process will take place on the 7th floor of the BMRC located at the Clinical Research Building in downtown Miami. The research coordinator will describe the study to the participants and will go over the consent forms to make sure there are no additional questions that were not answered. Participants will be asked to sign one copy of the consent form and be provided with a signed copy. This consent form will cover participation at during both sessions 1 and 2. Approximately 20 – 30 minutes will be devoted towards going over the consent and an unlimited time will be provided for questions and answers prior to signing the consent. Participants will also be informed that they are able to refer to primary care physicians and/or loved ones before providing consent to participate in the study. In addition, study referrals will be verbally consented in order to complete the pre-screening process using

Cognitively Impaired Adults

Prior to participation in session 1 of the study, at the pre-screening, our group will administer the Montreal Cognitive Assessment or Mini-Mental State Exam. Individuals scoring at levels indicative of gross cognitive dysfunction or dementia will be excluded from the study. Each assessment takes approximately 5 minutes to administer.

30) Process to Document Consent in Writing

Standard operating procedures will be followed in order to attain written documentation of consent in conjunction with (HRP-091).

31) Drugs or Devices

None

IRB Study Number: 20190760
Version: 10 Date: 06/06/2022

References

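### Table 1 marks the PCL-5, MMSE and MINI only at Session 1, the trauma-recall visit, while the text requires eligibility to be settled earlier

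*Combined protocol and SAP*

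**What the plan says.** The inclusion list in Section 6 requires "Elevated PTSD symptoms as assessed by the PCL-5 using a cut-off of 34 or above". The same section has pre-screening by phone, in person or online, with the PC-PTSD-5 given by phone, and then says: "Individuals meeting eligibility criteria will be then be invited to the Coral Gables campus". An in-house screener, which includes the MMSE, follows consent.

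Section 8 (General overview) says that women are consented once all eligibility criteria are met. Under Screening it places the five-item PC-PTSD-5 before consent and gives the reason: "This is required given trauma interventions can potentially have adverse effects on asymptomatic individuals". It also mentions an in-person screening session without listing its content. Section 29 places the MMSE, or the Montreal Cognitive Assessment, "Prior to participation in session 1 of the study, at the pre-screening".

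Table 1 has a T0 screening column with no mark in any row. The rows "Mini-mental State Exam screener", "Mini-International Neuropsychiatric Interview" and "PTSD Checklist for DSM-5 (PCL-5" each have one mark, at T1. There is no PC-PTSD-5 row.

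Section 8 describes Session 1 as intake, blood draw, mock scan, scan, second blood draw, self-compassion task and third blood draw. Then: "Following the compassion task a battery of psychosocial and neurocognitive measures will be administered".

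**The concern.** A screening instrument protects participants only if it is scored before the exposure it guards against. Section 17 rates the study as greater than minimal risk because of the recall of severe trauma. Section 15 says that psychiatric screening is there for safety after such recall. Staff who follow Table 1 would first give the PCL-5 at a fasting visit of about 4 to 5 hours that contains that recall.

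Two things are at stake. A woman who turns out to be below 34 may already have recorded her trauma, been scanned and given blood. And if the PCL-5 comes after recall, the score that decides entry is taken under conditions that the cut-off of 34 was not described for.

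**Working it through.** No sample size, power or error rate is involved, so the check compares the texts.

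**1. Is the empty T0 column an artefact of reading the PDF?** The header has 9 columns: domain, measure, and T0 to T6. The PCL-5, MMSE and MINI rows each have 9 fields, with the mark in the fourth, which is T1. The Subjective Unit of Distress row has marks from T1 through T6 and a blank at T0, so the alignment holds. Only the Health Markers rows lose a field (8 instead of 9), and they do not bear on this point. The empty T0 column is what the table shows.

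**2. Where does each instrument belong?**

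| Instrument | Role | Timing in the text | Table 1 |
|---|---|---|---|
| PC-PTSD-5 | Screen (Sections 6, 8) | Before consent | No row |
| PCL-5 | Inclusion criterion 2 (Section 6) | All criteria met before consent (Section 8); no specific time given | T1 only |
| MMSE | Exclusion for severe dementia (Section 6) | After consent (Section 6); before Session 1 (Section 29) | T1 only |
| MINI | Called screening data, used for suicide risk (Section 14) | No time given | T1 only |

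The only PTSD instrument with a stated time before Session 1 is the PC-PTSD-5, and it is not the one that defines inclusion.

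**3. What happens at T1?** In order: consent form completed; intake (body measurements, medical history, pre-scan mood); first blood draw; mock scan; scan, including 5 minutes of trauma recall; second blood draw; self-compassion task; third blood draw; psychosocial and neurocognitive battery. Section 10 adds that the personal trauma episodes are recorded during Session 1a, at the intake stage.

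**4. Where in T1 could the PCL-5 fall?**

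- *In the post-scan battery.* The intake list in Section 8 does not name it. Section 10 lists it under neuropsychological assessment. The post-scan self-report questionnaires refer the reader to Table 1. On this reading, recall and all three blood draws precede the eligibility score.
- *At intake.* Table 1 files the PCL-5 and MINI under Psychiatric and the MMSE under Cognitive, whereas the post-scan battery is described as psychosocial and neurocognitive. On this reading the scan comes later, but the order relative to script recording is unstated, and Section 8's rule that criteria are met before consent is still broken.
- *At a separate screening session.* Then the T1 mark is wrong and belongs under T0.

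The first reading has somewhat more support for the PCL-5. For the MMSE, Sections 6 and 29 point earlier; for the MINI, so does the word screening in Section 14. On each of the three readings, either Table 1 or the text has to change.

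**The case against.** The strongest reply is that a T1 mark names a visit, not an order within it. No section says that the PCL-5 follows the scan. The heading in Section 10 that names it fixes no time, since the same text runs on to the POMS given after each trauma session. Section 8 already states the safeguard: eligibility first, then consent, then procedures. On that view only a table needs tidying.

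Much of this stands. A reader might infer that the eligibility score is definitely taken after the scan and recall, but the documents only leave that open and, for the PCL-5, lean towards it. The sentence in Section 8 about harm must also be read narrowly. It concerns trauma interventions in asymptomatic people and justifies the PC-PTSD-5, which does come before consent. A woman who passes that screen and scores below 34 on the PCL-5 is not shown to be asymptomatic, and the sentence says nothing of MRI or blood draws.

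What does not stand is that the text already solves the problem. Its general rule needs a time at which the PCL-5 is given, and the only one stated is T1.

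**Conclusion.** The contradiction is established: T0 is blank, the PC-PTSD-5 has no row, and the PCL-5, MMSE and MINI are marked only at T1, against Sections 6, 8 and 29. The T1 mark is a stated schedule, and following it lets women enter the trauma-recall visit before inclusion criterion 2 is checked.

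The consequence cannot be sized. If 20% to 40% of women who pass the phone screen scored below 34, enrolling 36 would need 36/0.8 = 45 to 36/0.6 = 60 women, that is 9 to 24 ineligible. A reader might take this as the number exposed, but the failure rate is an assumption with no source in the documents, and the figure counts women completing Session 1 only if the PCL-5 is given after it. If the PCL-5 is given before the procedures and acted on, the number is zero. Nor do the documents support a claim that scores taken after recall read high: they give neither a standard deviation nor a recall effect.

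A reader might also infer exclusions after randomisation. Section 9 places randomisation at the second visit, so an ineligible woman can still be removed before it. The issue concerns participant protection and the eligibility threshold, not the validity of the randomised comparison.

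**What to change.** Reconcile Table 1 with Sections 6, 8, 10 and 29:

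- Add a PC-PTSD-5 row, marked at T0.
- Move the PCL-5, MMSE and MINI marks to T0. Where Section 6 requires consent first, as for the in-house screener with the MMSE, use an explicit step after consent and before any study procedure.
- Resolve the consent order itself, since Section 8 puts all eligibility before consent while Section 6 puts part of the screening after it.
- State when eligibility is confirmed relative to consent, trauma-script recording, scan and blood draw.
- Apply the same check to the acculturation scale (BASH) in inclusion criterion 4 and the ACTG interview in criterion 3, which are also first marked at T1.

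The instruments do not change. The cost is a protocol edit and slightly more screening time before Session 1, including staff time for the MINI, which is an interview.

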	*Self/other- compassion scales		X					X
	External and Internal Shame Scale (EISS)		X					X
	*HITS Intimate Partner Violence Screening Tool		X					X
	Religion & Spirituality Questionnaire		X					X
	Profile of Mood States		X	X	X	X	X	X
Neurocognitive	Trail Making Test		X					X
	Hopkins Verbal Learning Task		X					X
	Brief Visual Memory Test		X					X
	WAIS-R Digit Symbol Substitution		X					X
	WAIS-R Digit Span		X					X
	WAIS-R Letter Number Sequencing		X					X
	WAIS-R Block Design Test		X					X
	COWAT		X					X
			X					X
	Paced Auditory Serial Addition Test		X					X
	Rey Complex Figure Test		X					X
	Verbal Fluency Task		X					X
	Color-Word Interference test		X					X
	Grooved Pegboard		X					X
	Iowa Gambling Task		X					X
Behavioral	Adult (ACTG) structured interview		X					X
	Self-compassion task		X					X
Biomarker	Saliva for CORT or ACTH & sAA via ELISA		X					X
	Serum and plasma for NFkB & FBPK5		X					X
	Serum and plasma aliquots for storage		X					X

IRB Study Number: 20190760

Version: 10 Date: 06/06/2022

Health Markers							
	Review of systems		X				X
	Basic Demographic Questionnaire		X				X
	Pittsburgh Sleep Quality Index		X				X
	Physical Health Questionnaire		X				X

11) Specimen Banking*

Participants will be asked to abstain from illicit recreational substances, caffeinated and decaffeinated substances, aspirin and other medications, alcohol and strenuous exercise, and to fast from 10 pm on the night before arrival to the Behavioral Medical Research Center (BMRC) between 8 and 10 am before each visit. Participants will be advised to consult their physician before beginning the fast if the schedule varies from normal eating patterns. On the first visit, a urine toxicology screen (i.e., alcohol, barbiturates, benzodiazepines, LSD, PCP, THC, morphine, and amphetamines) will be performed. Urine samples will not be stored after analysis.

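### The pre-visit medication abstention in Section 11 does not say whether prescribed antiretroviral therapy is covered, and it is not reconciled with Sections 6 and 8

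*Combined protocol and SAP*

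**What the plan says.** Section 11 lists what participants should avoid before coming in. After illegal recreational drugs, which are named separately, the list continues with "caffeinated and decaffeinated substances, aspirin and other medications", and then alcohol and vigorous exercise. The same sentence asks them "to fast from 10 pm on the night before arrival" at the Behavioral Medical Research Center, with arrival "between 8 and 10 am before each visit". The next sentence adds the only safeguard: "Participants will be advised to consult their physician before beginning the fast if the schedule varies from normal eating patterns".

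Section 6, inclusion criterion 3, requires participants to be "on a stable anti-retroviral therapy regimen for > 6 months". Criterion 7 requires HIV-positive serostatus.

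Section 8 (General overview) carries its own version, placed directly after its description of the first and sixth sessions: "On the evening prior to these sessions participants will perform an overnight fast and told to avoid drugs, alcohol and exercise". It sends participants to the Cox Neuroscience Annex on those mornings.

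**The concern.** The inclusion criteria define the population by long-term use of a prescribed medicine. The specimen paragraph then asks the same women to abstain from medications without limiting the term. A participant or coordinator who follows Section 11 to the letter could take it to cover ART, and nothing in the paragraph directs her to ask a clinician about that. The wording also reaches other prescribed medicines. For example, Section 6 excludes only uncontrolled hypertension, so women treated for hypertension may be enrolled. Section 17 (Risks to Subjects) does not mention withheld medication.

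The main issue is participant safety. A secondary one is uniform conditions at sampling. Sessions 1 and 6 are when Table 1 schedules the saliva and blood markers, and staff working from two different rules may not prepare every woman in the same way.

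**Working it through.** The plan has no figure to reproduce on this point. The check sets the provisions side by side.

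| Feature | Section 8, General overview | Section 11, Specimen Banking |
|---|---|---|
| What is avoided | Drugs, alcohol, exercise | Illegal drugs, caffeinated and decaffeinated items, aspirin and other medicines, alcohol, strenuous exercise |
| Visits | Sessions 1 and 6 | Each visit |
| Start | Evening before | 10 pm for the fast; none given for medication |
| Site | Cox Neuroscience Annex | Behavioral Medical Research Center |
| Advice to see a physician | None | Only about the fast and eating pattern |
| Prescribed medicines or ART | Not addressed | Not addressed |

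1. **Does the Section 11 wording mean medicines?** Yes. Illegal substances have their own entry in the same list, and the phrase in question begins with aspirin. It cannot reasonably be read as street drugs only.

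2. **Does Section 8 settle the matter?** No. Its single word, drugs, could mean medicines, illegal substances or both. It neither confirms nor narrows Section 11.

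3. **Is there an exemption?** None appears in the protocol text. The consultation advice in Section 11 depends on whether fasting departs from usual eating, so it does not cover medication.

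4. **How long is the abstention?** The clock times give a fast of 10 hours (10 pm to 8 am) to 12 hours (10 pm to 10 am). The sentence attaches 10 pm to the fast. It does not say that the medication abstention shares that window, so its length is unstated.

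5. **Which visits?** Section 8 gives two. Taken alone, the wording of Section 11 could cover all six sessions. However, it is tied to a morning arrival on site, whereas Sections 8 and 9 describe writing sessions 2 to 5 as online. Sessions 1 and 6 are the supportable reading.

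6. **How many women?** If criteria 3 and 7 are applied as written, every enrolled participant is on ART, which is up to the planned 36. Section 3 refers to women with or without HIV, and the screening text in Section 8 foresees HIV-negative participants. The number on ART is therefore not fixed by the documents.

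**The case against.** The strongest reply is that this is a wording gap in a specimen-handling paragraph and does not touch the estimand, the randomisation or the analysis. Much of that stands, and several stronger readings should be set aside.

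- **That Section 11 contradicts the ART criterion.** A reader might infer this, but criterion 3 is an entry condition on regimen history. It does not govern dosing around visits, and a brief abstention would not make anyone fail it.
- **That women are told to miss doses.** The documents give no dosing times and no duration for the medication abstention. Whether a dose would be missed, delayed or unaffected cannot be determined from them.
- **That all six sessions are affected.** This is the least supported reading, for the reason given in step 5. Section 7 does mention a private office for the writing, so the setting is itself inconsistent, but that is thin support.
- **That biomarkers would be disturbed.** Nothing in the protocol links a short pause to NF-κB, FKBP5, ACTH or alpha-amylase. The instruction is the same in all three arms, and Section 8 applies its version at both sessions 1 and 6, so no route to bias between arms is evident.
- **That the antiretroviral interview would record non-adherence caused by the study.** Table 1 schedules the interview at T1 and T6, and the title of its cited source refers to adherence. The protocol uses it to assess the regimen, gives no recall window or scoring, and does not list adherence as an outcome.

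The site difference carries little weight on its own, because Section 21 allows both locations. Participant instructions or consent wording outside the public text may also contain an exemption; that cannot be judged here.

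What the reply does not remove is that the protocol states a rule which, followed literally, reaches a medicine that its own criteria require, and states it in two ways.

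**Conclusion.** The point holds as an unreconciled ambiguity bearing on participant safety. Section 11 gives an unqualified medication abstention with no duration, Section 6 requires stable ART, and Section 8 gives a different pre-visit rule. It applies to women on ART at sessions 1 and 6. No statistical quantity in the plan changes, and no size can be put on any effect on the outcomes: the biomarker and interview consequences remain possible but not shown.

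The conclusion rests on two assumptions: that the term in Section 11 means medicines, which its own list supports, and that no exemption exists in participant-facing text that is not public. If one does exist there, the protocol still needs to agree with it. The matter merits correction because the remedy is cheap and the ambiguity concerns safety. No view is taken here on which medication rule is right.

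**What to change.** Reconcile Sections 6, 8 and 11 into one pre-visit instruction that states:

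- whether prescribed medicines, including ART, are covered;
- which visits it applies to;
- over what window, given separately for the fast and for any medication abstention;
- at which site.

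Use the same text in Sections 8 and 11 and in the participant instructions. The study physician should settle the clinical content.

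The cost is about one sentence in each place. Sample size, randomisation, schedule and analysis are unchanged.
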